Developing a psychological understanding of idiopathic drop attacks

Study Protocol

Version 3

[name]

15th January 2018

1 Introduction

Idiopathic drop attacks (IDAs) have been defined as falls to the floor without warning, where there is no identified organic cause, despite diagnostic testing. They are not caused by malfunction of the lower limbs, changes in body or head posture, or vertigo. There is also no loss of consciousness and recovery is rapid. Despite this fast recovery, people can experience significant injuries and fear about further falls, impacting on their everyday functioning.

This phenomenon was highlighted by Stevens and Matthews (1973) who recruited 33 patients from a neurology clinic and seven from a gynaecological clinic. They also approached 100 men who were admitted for routine surgery but found that none of these had experienced drop attacks. Therefore their sample was entirely female, with onset occurring on average at age 44. Although the age-range of onset spanned from 19 to 69, in two thirds of the sample onset was between the ages of 40 and 59.

The authors ruled out obesity, vascular disease, epilepsy, vestibular disease, limb weakness and hypothyroidism as contributing to IDAs. They investigated hormonal changes, given that the age of onset coincided with when menopause could be likely to start and due to the fact that 60% of the younger patients had onset of IDAs during pregnancy. Despite this, the authors found no clear links between hormonal changes and IDAs, although 45% did experience onset either during pregnancy or within 3 years either side of the start of the menopause.

The frequency of IDAs varied greatly between individuals but ranged from two to more than 12 falls per year, usually while walking. This was more likely to happen when out of the house but over half of the sample also reported falling at home. These falls would lead to injury to the knees and often also to the hands, chest and face. 18% reported having fractured or broken bones as a result of an IDA. Given the age of onset, the increased likelihood of osteoporosis would also increase the risk of more severe injury as a result of IDAs. The authors also reported that many women would become afraid to go out due to both the risk of injury and embarrassment.

Although it is undocumented, the prevalence of IDAs could be relatively high. As part of their recruitment process, the Stevens and Matthews (1973) asked 200 consecutive patients at a gynaecology clinic whether they had experienced falls and found that 3.5% met the criteria for IDA. This suggests that this phenomenon could account for a significant number of falls in women in the general population.

There are similarities between IDAs and psychogenic non-epileptic seizures (PNES). However, IDAs are not included widely included in studies of PNES, which tend to focus on 'convulsive' seizures. Hubsch et al. (2011) analysed clinical signs in 145 PNES and identified different subtypes of seizure, none of which covered IDAs. However, Galimberti et al (2003) and Devinsky et al (1996) included patients with IDA within a PNES sample, accounting for around 10% of each sample. There has been no published research investigating this group in isolation since Stevens and Matthew's (1973) study other than a small number of case reports (Butsch & Schneemann, 2014), one of which identified a woman's IDAs as occurring following recollection of traumatic experiences, suggesting a psychological mechanism (Wilner et al., 2010).

A paper which is currently being prepared for submission by [name], [name] & [name] at the Department of Clinical Neurosciences, Edinburgh, identified 83 patients who had attended a neurology clinic over nine years who described experiencing these attacks. This led the authors to develop a hypothesis that IDAs are a conditioned behavioural response to negative external (environmental or situational) or internal (anxiety symptoms or dissociation) stimuli. This association is maintained through fear of collapse and/or through the fall providing relief from the negative stimuli. This type of mechanism has been highlighted previously in functional neurological disorders, where limbic regions were found to have a greater influence on motor preparatory regions when in a state of arousal (Voonet al., 2011).

As the underlying mechanism of IDAs is unknown, there is currently no treatment available. However, Hoeritzauer and colleagues report that a small number of patients saw their IDAs resolve following an explanation of the episodes as conditioned responses and the use of distraction techniques. A psychological understanding of the problem could help to identify a potential psychological intervention. Such interventions have been found to be effective for PNES, particularly cognitive behavioural therapy (Goldstein et al., 2010). This type of intervention could focus on helping individuals to manage their condition and improve the ways they cope with the anxiety surrounding future falls, rather than necessarily seek to resolve the IDAs.

This research aims to explore a psychological understanding of drop attacks. This will be investigated through the collection of qualitative data from interviews and recorded diaries from individuals experiencing IDAs. The data will be analysed using a grounded theory approach in order to better understand the onset of drop attacks, the impact of life stressors as well as thoughts, feelings and behaviour both directly before and after a IDA.

2 Aims

The main aim of this research is to develop a psychological understanding of idiopathic drop attacks. The primary research question is as follows:

- What are the predisposing and precipitating factors related to the onset of IDAs?

Secondary research questions are:

- What are individuals' thoughts, emotions and behaviour immediately prior to an IDA?
- What are individuals' thoughts, emotions and behaviour immediately following an IDA?

3 Methods

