3.2 Design

In this exploratory qualitative study, neurology outpatients with ongoing IDAs will undergo psychological assessment and complete written diaries for eight weeks. Throughout the study, participants will receive treatment as usual from a neurologist.

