3.3 Procedure

Participants will be recruited from a neurology outpatient clinic at the Department of Clinical Neurosciences in Edinburgh where they will be approached by their consultant who will give them a participant information sheet. If they are interested in taking part, a meeting will be set up with the researcher to discuss the study further and obtain written informed consent.

Participants will then meet with the researcher to complete an initial psychological interview which will be audio recorded. This interview will follow a standard initial psychological interview structure and will aim to gain information about the person's experiences of IDAs, along with relevant personal and social history. The interview schedule is included in appendix 1.

Following this initial interview, participants will be asked to record written accounts of any IDA, detailing their thoughts, physical arousal, feelings and behaviour, as close to the event

as possible. They will be encouraged to record detailed accounts, outlining the period before, during and after the episode, in order to identify any potential triggers. They will be shown an example of a completed diary in order to help them to understand what they need to do. Participants will be asked to record such events over a period of eight weeks during which the researcher will contact them fortnightly to discuss any difficulties or concerns. If participants do not experience any drop attacks during this period, they will be asked if they want to continue recording diaries for an additional two to four weeks.

Following completion of this period, participants will meet again with the researcher to return the diaries and discuss any patterns noticed in the interview and diaries. The researcher will also answer any further questions that the participant has about the study.

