3.4.2 IDA record

Participants will be asked to write an account of any IDAs. They will be shown an example diary and will also be given a prompt sheet, asking them to recall any triggers, feelings, physical arousal, thoughts and behaviour both directly before and after the episode. This diary will be completed by participants as close to the episode as possible.

4 Sample size

In order to address all three of the research questions, a qualitative approach will be used. An overall sample size of ten should be sufficient to allow themes to be identified. A purposive sampling method will be used to recruit younger participants as well as those who are in the average age range for onset. This will allow any differences between these two groups to be explored further. As the inclusion criteria specifies 6+ IDAs per year, this will ensure a fairly homogenous sample in terms of frequency of IDAs.

There is a sample of approximately 40 patients who had ongoing drop attacks in July 2016 which can be recruited from. One to two new referrals per month are currently being made to

[name], and these patients can also be approached. This is a relatively small pool and there can be some unwillingness to engage with a psychological approach within the functional neurological population. However, as this study is aiming to help better understand participants' experiences, rather than investigating psychological treatment, this may enhance engagement. Attrition is also a factor but, as the primary research question relies on information from the initial interview, the risk of this is reduced. Therefore, recruiting a purposive sample of ten participants should be achievable.

5 Analysis

The content of the psychological interviews and diaries will be analysed using a grounded theory approach in order to meet all of the study objectives. Using both initial interviews and recorded accounts will allow information to be obtained from different viewpoints, enriching the data. This data will be coded by initially naming each segment of data and then synthesising the most common codes to identify themes. From these, theories can be developed regarding predisposing and precipitating factors. Themes regarding thoughts, emotions and behaviour can also be explored.

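### The protocol body neither records nor uses whether a participant has already been given the clinic's conditioned-response explanation, so a learned account cannot be told from a spontaneous one

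*Protocol*

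**What the plan says.** The Introduction (Section 1) describes a paper in preparation from the Edinburgh department, based on 83 clinic patients seen over nine years. Of that work it says: "This led the authors to develop a hypothesis that IDAs are a conditioned behavioural response". The stimuli may be external or internal, and the link is held to persist through fear of falling, through relief that the fall brings, or both. The same section then says that a small number of patients improved after being given this account of their attacks together with distraction advice: "following an explanation of the episodes as conditioned responses and the use of distraction techniques".

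Section 3.3 takes the participants from the same place: "Participants will be recruited from a neurology outpatient clinic at the Department of Clinical Neurosciences in Edinburgh". Their own consultant approaches them. Section 4 names two sources: "approximately 40 patients who had ongoing drop attacks in July 2016", and one to two new referrals a month. Section 3.2 adds that "participants will receive treatment as usual from a neurologist" for the whole study and does not say what this contains.

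Eligibility (Section 3.1) requires ongoing attacks at least six times a year and has one exclusion, an alternative diagnosis. Purposive sampling (Section 4) is by age. Section 5 codes interviews and diaries, builds themes from the codes that occur most often, and has participants say whether they agree with the themes.

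**The concern.** The study is meant to build a psychological account of the attacks from what participants say and write. The hypothesis and the research questions cover much of the same ground: what sets an attack off, and what is thought, felt and done just before and after it. A person who has been told in clinic that attacks are conditioned responses may look for triggers, arousal and relief, and report them in those terms. The diary prompt asks about triggers and arousal, which makes this easier.

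If that happens and exposure is not known, a theme of trigger, anxiety or relief has two possible sources, the participant's own experience or the explanation received. What is at stake is how such a theme may be interpreted when the findings are written up. The part of the primary question on precipitating factors and both secondary questions are affected. Predisposing factors drawn from personal and social history are less so.

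**Working it through.** The protocol gives no figure for exposure, and the sample of ten rests on judgement, so there is no planned figure to reproduce. The check is to set the sections side by side and then show what different exposure shares would mean.

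**Step 1. Can exposed people be in the sample?**
- Same department for hypothesis and recruitment: Introduction and Section 3.3. Stated.
- Explanation given to some patients: Introduction. Stated, but only for a small number, and those are patients who improved.
- Opportunity for exposure before interview: Section 4 dates the existing pool to July 2016 and Section 6 starts recruitment in January 2018, a gap of 18 months.
- Opportunity during the study: Section 3.2, with content not described.
- Barrier to entry: Section 3.1 shuts out people whose attacks have resolved and stayed resolved. It does not shut out people who were told and still have attacks.

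Exposed participants are therefore possible but not documented.

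**Step 2. Would the plan notice them?**
- Eligibility, the described interview content (3.4.1), the diary (3.4.2) and sampling (4) do not mention earlier explanations. Appendix 1 was not available, so this is confirmed for the protocol body only.
- Building themes from frequent codes does not separate a shared experience from a shared explanation.
- Agreement with the themes does not separate them either. Someone who has accepted the explanation would be expected to agree with a theme that restates it.

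**Step 3. Illustration under an assumed exposed share p.** The expected number exposed among ten is 10p. The chance of at least one is 1 − (1 − p)^10 for independent draws, and 1 − C(40 − 40p, 10)/C(40, 10) when ten are drawn at random from the 40 without replacement.

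| Assumed p | Expected exposed (10p) | At least one, independent | At least one, from 40 |
|---|---|---|---|
| 0.05 | 0.5 | 40% | 44% |
| 0.10 | 1.0 | 65% | 70% |
| 0.25 | 2.5 | 94% | 96% |
| 0.50 | 5.0 | 99.9% | above 99.9% |

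For example, at p = 0.05 two of the 40 are exposed, and 1 − (30 × 29)/(40 × 39) = 1 − 870/1560 = 44%. Sampling is purposive rather than random, so the table shows scale and is not a prediction. At p = 0 the problem does not arise. Even a modest share would make at least one exposed participant likely, but one or two among ten would have a limited effect on the themes.

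**The case against.** The strongest reply is that the only patients documented as having had the explanation are those whose attacks then stopped, and most of them could not enter. Nothing says that patients with continuing attacks were told. This stands, and it is why the number exposed may be small.

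A second reply is that the study is exploratory. Its aims do not name the conditioned-response hypothesis, and it collects biographical history and diaries written close to each event. This also stands in part: it narrows the risk to precipitants and to accounts just before and after attacks. Diaries can still be shaped by an explanation already received.

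A reader might infer more than the text supports:
- **That the clinic routinely gives this explanation, or that it is part of treatment as usual.** Neither is stated.
- **That half or more of the ten will have been told, so that the theory is circular.** No share is given. The possible range is 0% to 100%, and the only wording points to few patients. Nor does being told mean that a participant will repeat the explanation.
- **That the July 2016 patients are the main source, or are the same people as the 83.** Overlap is plausible but not stated, and Section 4 does not rank the two sources.
- **That saying no treatment exists contradicts treatment as usual.** The absence of a specific treatment for drop attacks is compatible with ordinary neurology follow-up.
- **That sampling should be by exposure, with separate coding and a rule discounting themes seen only in exposed people.** These are debatable in a grounded theory study of ten that already plans an age comparison. New referrals cannot be assumed unexposed, and not all could finish. With diaries of 8 to 12 weeks and data collection ending in December 2018, about 9 to 10 months of referrals at one to two a month gives roughly 9 to 20 people, before eligibility and consent.

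**Conclusion.** The point holds as a gap in what the study will be able to conclude. It does not show bias. With exposure unrecorded, the plan as written could not tell a reader whether a trigger, anxiety or relief theme also arises in people who were never given the explanation. The effect could range from nil to substantial, and the documents do not allow it to be narrowed.

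This rests on three assumptions: that some people with continuing attacks have been given the explanation, or will be during the study; that being told can colour later accounts; and that appendix 1 contains no question that already covers this. If appendix 1 does ask about earlier explanations, the recording gap shrinks, but Section 5 still makes no use of the answer. The change is a low-cost improvement and not a condition for the study to proceed.

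**What to change.** **Section 3.3.** Before the interview, record from clinic notes or the consultant whether, and when, each participant was given the conditioned-response explanation or distraction advice. At the end of the diary period, check the same source for anything given since. Do not ask the participant, because the question could plant the idea it is meant to trace.

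**Section 5.** Code all data together as planned. For each trigger, anxiety or relief theme, report how many exposed and how many unexposed participants support it. Describe a theme seen only in exposed participants as possibly reflecting the explanation received.

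**Cost.** A short notes check, which the procedure does not now include, and one extra breakdown in the theme table. No added participants. The groups will be small, so the breakdown is descriptive only, and notes may not capture every conversation in clinic.

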3.1 Participants

Participants will be ten individuals who are experiencing ongoing IDAs. Inclusion criteria are 1) Aged 18+, 2) IDAs occurring 6+ times per year, 3) Able to provide informed consent.

Exclusion criteria are 1) Diagnosis which would provide an alternative explanation for drop attacks.

3.2 Design

In this exploratory qualitative study, neurology outpatients with ongoing IDAs will undergo psychological assessment and complete written diaries for eight weeks. Throughout the study, participants will receive treatment as usual from a neurologist.

3.3 Procedure

Participants will be recruited from a neurology outpatient clinic at the Department of Clinical Neurosciences in Edinburgh where they will be approached by their consultant who will give them a participant information sheet. If they are interested in taking part, a meeting will be set up with the researcher to discuss the study further and obtain written informed consent.

Participants will then meet with the researcher to complete an initial psychological interview which will be audio recorded. This interview will follow a standard initial psychological interview structure and will aim to gain information about the person's experiences of IDAs, along with relevant personal and social history. The interview schedule is included in appendix 1.

Following this initial interview, participants will be asked to record written accounts of any IDA, detailing their thoughts, physical arousal, feelings and behaviour, as close to the event

as possible. They will be encouraged to record detailed accounts, outlining the period before, during and after the episode, in order to identify any potential triggers. They will be shown an example of a completed diary in order to help them to understand what they need to do. Participants will be asked to record such events over a period of eight weeks during which the researcher will contact them fortnightly to discuss any difficulties or concerns. If participants do not experience any drop attacks during this period, they will be asked if they want to continue recording diaries for an additional two to four weeks.

Following completion of this period, participants will meet again with the researcher to return the diaries and discuss any patterns noticed in the interview and diaries. The researcher will also answer any further questions that the participant has about the study.

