3.4 Measures

3.4.1 Semi-structured assessment interview

This audio-recorded 60-minute interview will follow the format of an initial psychological assessment and will allow discussion of presenting problems and relevant personal and social history. This will allow potential predisposing and precipitating factors to be identified. Participants' experiences of IDAs will also be discussed, focussing on thoughts, feelings and behaviour before and after the episodes. The participants will also be asked about the impact that these have had on their everyday functioning.

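### Does a diary filled in only after an attack need attack-free entries before it can be used to look for triggers?

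*Protocol*

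**What the plan says.** Section 3.3 has participants keep written accounts of attacks for eight weeks, "outlining the period before, during and after the episode, in order to identify any potential triggers". Section 3.4.2 defines the measure in the same way: "Participants will be asked to write an account of any IDAs", with a prompt sheet "asking them to recall any triggers, feelings, physical arousal, thoughts and behaviour both directly before and after the episode". Section 3.2 speaks more loosely of diaries kept for eight weeks. Sections 3.3 and 3.4.2 make clear that the content is attack accounts only.

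The primary question in section 2 is "What are the predisposing and precipitating factors related to the onset of IDAs". The secondary questions ask what people think, feel and do just before and just after an attack. Of the initial interview, section 3.4.1 says: "This will allow potential predisposing and precipitating factors to be identified". Section 4 adds that the primary question depends on that interview.

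Under section 5 the "psychological interviews and diaries will be analysed using a grounded theory approach in order to meet all of the study objectives". Coding proceeds by "synthesising the most common codes to identify themes. From these, theories can be developed regarding predisposing and precipitating factors".

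**The concern.** A diary opened only by an attack has no reference level. Suppose anxiety is coded in most entries. It may precede attacks in particular, or the person may be anxious much of the time, and the diary looks the same either way. A rule that promotes the most common codes to themes favours states that are common in general.

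This could matter because the hypothesis reported in section 1 is that "IDAs are a conditioned behavioural response to negative external (environmental or situational) or internal (anxiety symptoms or dissociation) stimuli". Section 1 also says that people with these attacks can come to fear further falls, so frequent anxiety is plausible whether or not it sets off attacks. Frequent anxiety codes could then be read as support for the hypothesis. Attack-free entries cannot be recovered once the diary period is over, so the choice has to be made before diaries start.

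**Working it through.** The protocol gives no figure to reproduce. The sample of ten is a judgement about themes, with no error rate, power or effect size. The checks below take from the protocol 10 participants (sections 3.1 and 4), at least 6 attacks per year (section 3.1), 8 weeks of diary, an optional extension of up to 4 weeks for those with no attack, and fortnightly contacts (section 3.3). All shares, the rate of 12 per year and the Poisson model are assumptions.

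**1. What attack-only entries can show.** Let p be the share of attack entries naming a state and b the share of time spent in it. The attack rate ratio is [p/(1−p)] / [b/(1−b)].
- With p = 0.60 the numerator is 0.60/0.40 = 1.5.
- Ratio 1 needs b = 0.60.
- Ratio 2 needs odds of 1.5/2 = 0.75, so b = 0.75/1.75 = 0.43.
- With p = 0.70, the ratio is 5.4, 2.3, 1.0 or 0.26 for b = 0.30, 0.50, 0.70 or 0.90.

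The diary supplies p and not b, so it leaves even the direction of association open. The logical point is correct.

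**2. How many attack entries to expect.** The mean per person is rate × 8/52.

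| | 6 per year | 12 per year |
|---|---|---|
| Mean per person | 0.923 | 1.846 |
| Entries from 10 people | 9.2 | 18.5 |
| P(no entry) = exp(−mean) | 0.397 | 0.158 |
| People with at least one | 6.0 | 8.4 |
| People with two or more | 2.4 | 5.5 |

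At the floor, if everyone without an attack accepted the full extension, it would add 10 × 0.397 × 6 × 4/52 = 1.8 entries, for a total of about 11.

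**3. What attack-free entries would add.** One entry at each of three or four fortnightly contacts gives 10 × 3 = 30 to 10 × 4 = 40. Take 40 entries, p = 0.60, b = 0.4286 (true ratio 2), and treat entries as independent.
- Floor: the cells are 9.23 × 0.60 = 5.54, 9.23 × 0.40 = 3.69, 40 × 0.4286 = 17.14 and 40 × 0.5714 = 22.86. SE(log ratio) = √(1/5.54 + 1/3.69 + 1/17.14 + 1/22.86) = 0.744. The 95% interval is exp(0.693 ± 1.96 × 0.744) = 0.47 to 8.6.
- 12 per year: the cells are 11.08, 7.38, 17.14 and 22.86. SE = 0.573 and the interval is 0.65 to 6.1.
- With 30 attack-free entries the intervals are 0.45 to 9.0 and 0.62 to 6.5.

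None of these intervals separates a doubled rate from no association. Clustering within person is ignored.

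**4. Whether the study needs the missing quantity.** Set against the aims, the gap touches little:
- The secondary questions ask what surrounds an attack, which attack accounts describe directly.
- The primary question is assigned to the interview.
- No test, ratio or confirmation of the hypothesis is planned.

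**The case for a change.** The strongest case for a change is that section 5 does not carry over the cautious wording of section 3.3. It pools diaries with interviews for all objectives and moves from common codes to theories of precipitating factors. Participants' review of the themes cannot repair this, since agreeing with a theme says nothing about attack-free times. One short entry per existing contact needs no new visit. If even that is too much, relabelling diary findings as perceived antecedents costs nothing.

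Part of this stands. Nothing in the protocol supplies a background share, and some diary material may reach the theories of precipitating factors. The remedies gain little, however:
- **Relabelling.** The protocol already uses the qualifier potential in both section 3.3 and section 3.4.1, so perceived antecedents is close to a synonym and alters no result.
- **Attack-free entries.** The question is what is usual for a given person. At the floor about 4 of 10 people would have no attack entry and only about 2 would have two or more, so much of the comparison would fall back on pooled background, which does not answer it. Moments fixed around scheduled contacts would also differ from attack moments for trivial reasons. Section 1 reports that falls usually happen while walking and more often away from home, so an apparent contrast could mislead.
- **Burden.** The 30 to 40 extra entries would be asked of a pool that section 4 calls small and in part reluctant to engage with a psychological approach.

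A qualitative analyst also has other material to weigh. The interview covers presenting problems, history and everyday functioning, and patterns are discussed with each participant at the closing meeting.

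**Conclusion.** No change to the plan follows. Attack-only diaries cannot establish that a state is specific to attacks, but the study neither claims nor needs that. Following the protocol as written gives no wrong answer to its primary or secondary questions, and no stated figure or rule is in error. Attack-free entries are an optional design choice with a real cost and little return: 30 to 40 entries to set beside about 9 at the floor or about 18 at 12 attacks per year, with no usable ratio in either case.

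What stands is a caution for whoever writes the report: frequent diary codes are candidate triggers, in keeping with section 3.3, and their frequency alone is not evidence for the conditioned-response hypothesis.

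The counts rest on a Poisson model at the stated minimum rate, or at an assumed 12 per year; participants with more frequent attacks would contribute more entries. The shares of 60% and 70% and the background shares are illustrative. The interview schedule and prompt sheet are not in the document at hand and may already ask about a participant's usual state.

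### Is the voluntary two-to-four-week diary extension in Section 3.3 too short for an entry threshold of six IDAs per year?

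*Protocol*

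**What the plan says.** Section 3.1 of the protocol admits adults with "IDAs occurring 6+ times per year" and sets no upper limit. Section 3.3 fixes the diary: "Participants will be asked to record such events over a period of eight weeks during which the researcher will contact them fortnightly". For a participant with no IDA in that time, "they will be asked if they want to continue recording diaries for an additional two to four weeks". The longest diary is therefore 12 weeks. The extension is voluntary, and no second offer is described.

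Section 3.4.2 asks for near-event recording: "This diary will be completed by participants as close to the episode as possible". Section 5 explains why two sources are used: "Using both initial interviews and recorded accounts will allow information to be obtained from different viewpoints, enriching the data". Section 3.4.1 has the initial interview cover every participant's IDAs, "focussing on thoughts, feelings and behaviour before and after the episodes". Section 4 says that the primary question draws on that interview, and it warns that "there can be some unwillingness to engage with a psychological approach within the functional neurological population".

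The only information on rates is in Section 1, from an earlier clinical series in which frequency "ranged from two to more than 12 falls per year". The protocol gives no expected number of empty diaries and no target number of written accounts.

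**The concern.** Set side by side, the entry threshold and the diary length look mismatched. A participant at six IDAs per year has a mean gap of 8.67 weeks. That is longer than the whole eight-week diary and more than twice the longest extension. Such a participant could easily return an empty diary, and the extension would often not rescue it.

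The diary is the only source written close to the event. Both secondary questions ask what people think, feel and do immediately before and after an IDA, which is where later recall is least reliable. The sample is ten, and Section 4 wants to explore differences between younger participants and those in the usual onset range, so one or two empty diaries would be noticeable. The natural suggestion is to let the offer be renewed, for example up to 20 weeks in total.

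**Working it through.** **Inputs from the protocol.** Minimum rate 6 per year and ten participants (Section 3.1); eight weeks plus two to four (Section 3.3); data collection ends December 2018 (Section 6).

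**Assumptions, because the protocol gives no figures.** Poisson timing. Rates all at 6 per year, spread evenly over 6 to 12, or all at 12. Everyone accepts a full four-week extension. The comparison is a renewable offer up to 20 weeks. That cap is not in the protocol: it is the first even-numbered week at which fewer than 10% of diaries are empty at 6 per year (12.5% at 18 weeks, 9.9% at 20).

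The protocol states no probability of its own, so there is none to reproduce.

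**1. Share of empty diaries.** At rate r per year and w weeks, P0(w) = exp(−r·w/52). For an even spread over 6 to 12 it is [exp(−6w/52) − exp(−12w/52)] / (6w/52). At 12 weeks and 6 per year, exp(−1.385) = 0.250. For the spread, (0.2504 − 0.0627)/1.3846 = 0.136.

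| Rate per year | 8 weeks | 10 weeks | 12 weeks | 20 weeks |
|---|---|---|---|---|
| all at 6 | 39.7% | 31.5% | 25.0% | 9.9% |
| even over 6–12 | 25.9% | 18.7% | 13.6% | 3.9% |
| all at 12 | 15.8% | 9.9% | 6.3% | 1.0% |

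At 6 per year, the extension brings a first IDA to 1 − exp(−6×2/52) = 21% (two weeks) or 1 − exp(−6×4/52) = 37% (four weeks) of those with an empty diary. If rates spread evenly over 6 to 24, 5.9% are empty at 12 weeks.

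**2. Number of written accounts.** Themes are built from pooled accounts, so their number matters as well as the share of empty diaries. Expected accounts from ten participants:

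- Plan as written: 10 × [8r/52 + P0(8) × 4r/52]. At 6 per year: 10 × [0.923 + 0.397 × 0.462] = 11.1.
- Renewable, stopping at the first IDA or 20 weeks: 10 × [8r/52 + P0(8) × (1 − exp(−12r/52))]. At 6 per year: 10 × [0.923 + 0.397 × 0.750] = 12.2.

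| Rate per year | Eight weeks only | Plan with four-week extension | Renewable to 20 weeks | Gain over plan |
|---|---|---|---|---|
| all at 6 | 9.2 | 11.1 | 12.2 | about 1 |
| even over 6–12 | 13.8 | 15.6 | 16.1 | about 0.5 |
| all at 12 | 18.5 | 19.9 | 19.9 | about 0 |

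**3. Uptake.** Let a be the chance of accepting each four-week offer and q = exp(−4r/52). The plan leaves P0(8) × [(1−a) + aq] empty. Renewal leaves P0(8) × [(1−a) + aq(1−a) + (aq)²(1−a) + (aq)³].

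| Acceptance per offer | At 6 per year: plan / renewable | Even over 6–12: plan / renewable |
|---|---|---|
| 100% | 25.0% / 9.9% | 13.6% / 3.9% |
| 75% | 28.7% / 21.0% | 16.7% / 11.7% |
| 50% | 32.4% / 29.3% | 19.8% / 17.8% |

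At 50%, the gain in ten participants is 10 × (0.324 − 0.293) = 0.3 contributors at 6 per year and 10 × (0.198 − 0.178) = 0.2 over 6–12. At 12 per year, P0(8) = 0.158 and q = 0.397 give 0.110 against 0.099, a gain of 0.1.

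**4. Timing.** With evenly spaced IDAs at 6 per year and a random start, 1 − 8/8.67 = 7.7% are empty at eight weeks and none from ten weeks on, so renewal gains nothing. With clustered IDAs (negative binomial, empty share (1 + m/k)^(−k), where m is the expected count), 42% are empty at 12 weeks and 30% at 20 for k = 1, and 52% and 42% for k = 0.5.

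**5. What the text commits to.** Section 3.3 asks for accounts of whatever IDAs occur. No section promises an account from everyone, states a minimum number, or claims that 12 weeks will capture an IDA in each participant. Empty diaries are expected and have a stated response.

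**The case for a change.** The strongest case for the concern is that the 12-week figures already favour the protocol. They assume that everyone accepts and gets the full four weeks. A two-week extension leaves 19% to 32% empty (even spread to threshold), and half uptake of four weeks leaves 20% to 32%. Even with full uptake, the chance that three or more of ten diaries stay empty is 14% to 48%. The interview covers the same ground only in retrospect, the loss falls on lower-frequency participants, and Section 3.3 does not say what follows if the diary is still empty. Renewal would be voluntary and cheap: stopping at the first IDA, mean diary length would rise from 9.6 to 10.6 weeks at the threshold and from 9.0 to 9.4 over 6 to 12 per year.

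The arithmetic stands, and so does the observation that some near-event material may be lost. A team could reasonably choose a longer diary. What does not follow is that the present choice is wrong. The 25% figure puts all ten participants exactly at the minimum, whereas the criterion is open-ended and the cited range passes 12 per year. The large reduction at 20 weeks needs near-complete acceptance of repeated offers, in a pool that Section 4 calls relatively small and partly reluctant, with attrition a factor. Clustering raises the empty share, but it also leaves 30% to 42% empty at 20 weeks.

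The costs are also not trivial. If accepted four-week blocks ran in full, mean length at the threshold would be 8 + 4 × (0.397 + 0.250 + 0.158) = 11.2 weeks. Expected accounts would then also rise, to about 12.9. Counting back from 31 December 2018, a 20-week diary fits only if started by 13 August, against 8 October for 12 weeks.

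**Conclusion.** The concern does not hold. Followed as written, the plan gives an interview on the primary and both secondary questions from every participant. It also gives about 11 to 20 written accounts from ten people under Poisson timing with full uptake, and still about 9 to 18 if nobody extends. A renewable offer to 20 weeks, ending at the first IDA, would add between none and about one account. In contributors, it would add 10 × (0.250 − 0.099) = 1.5 of ten at most under Poisson timing (everyone at the threshold and accepting every offer), 0.1 to 0.3 with half accepting each offer, and none if IDAs are evenly spaced.

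These sizes rest on rates, timing and uptake that the protocol does not give. The conclusion does not depend on them: no statement in the protocol is contradicted, and none of its aims needs an account from each participant. Diary length trades burden and dropout against a small yield of extra near-event material. The protocol chose a modest voluntary extension, and reasonable reviewers could differ on its length.
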